5.3 Low Molecular Weight Iron Dextran (LMWID) or Ferric Carboxymaltose (INJECTAFER) Infusion

Volunteers will be admitted to the Columbia General Clinical Research Center (GCRC) (supported by the Columbia Clinical and Translational Science Award (CTSA) on Harkness Pavillion 10). One peripheral intravenous line will be inserted and blood (2 tubes, 10mL) will be drawn for determining the 24-hour post-transfusion recovery. The allowable time frame for this blood draw will be from 20-28 hours of infusion the prior day. The subject will be randomized from this point to 4-weeks later by the research pharmacy. A research pharmacist will provide the placebo (IV saline) or treatment (IV low molecular weight iron-dextran or ferric carboxymaltose) and test dose (25 mg LMWID, 12.5 mL of a 2 mg/mL solution of iron dextran or 0.5 mL of 50 mg/mL solution of ferric carboxymaltose, diluted in normal saline) in tinted infusion bags and tubing specifically designed to maintain blinding in clinical research studies (Medipak). If low molecular weight iron dextran is unavailable due to shortages, the research pharmacist will provide ferric carboxymaltose instead. A research nurse unaffiliated with the study team, from the Outpatient or Inpatient Center at the Columbia General Clinical Research Center (Harkness Pavillion 10th Floor), will be responsible for the test infusion and total dose iron infusion. The research pharmacy will provide a standard 1-gram dose of low molecular weight iron-dextran, ferric carboxymaltose, or saline in special bags designed to conceal group assignment. In addition, the clinical pharmacy will provide Solumedrol 125

Using this formula, the minimum dose that would be required to raise the hemoglobin by 2 g/dL would be ~800mg (minimum donation requirement is 110lbs = 50 kg) in a female and almost 900mg in a male. Thus, given that all subjects will be healthy volunteers with ferritin < 15 ng/mL with evidence of iron-deficient erythropoiesis, and will be dosed following a whole blood donation for study purposes, 1 gram of LMWID was chosen for simplicity, safety, consistency, and design considerations. Based on similar considerations, 1 gram of ferric carboxymaltose would provide equivalent total dose iron repletion with a similar safety profile.⁴²

5.4 Cognitive and Emotional Status Assessment

As outlined in the *Schedule of Measurements* section below, cognitive and emotional functioning will be assessed with a thorough battery of neuropsychological tests and questionnaires assessing overall wellbeing. Tests will be administered in person by a psychometrician who has received training on test administration.

Neuropsychological tests will be administered to subjects on an iPad or Tablet. Subjects will be supervised at all times during this portion of the evaluation and will be encouraged to complete the tests within one session (i.e. without interruption). Total time for test administration is approximately 30 minutes and the time of start and completion of the test battery will be recorded. When the neuropsychological battery has been completed, the subject will be provided with a clipboard containing printed copies of four questionnaires (see appendices 4-7). The subject will be asked to complete the surveys on his/her own without interruption. The time of start and completion of the surveys will be recorded.

Neuropsychological tests included were selected based on the following criteria: All (1) meet high psychometric standards, (i.e. are reliable, valid, and well standardized); (2) have appropriate normative data; (3) maintain the lowest potential

for patient burden, e.g. duration; (4) can be administered serially without significant practice effects.

5.4.1 Cognition

Subjects will be administered subtests from the NIH Toolbox Cognition Battery (NIHTB-CB), a computerized battery of neuropsychological tests. The NIH Toolbox provides a standard set of royalty-free, comprehensive assessment tools that can be used by researchers and clinicians in a variety of settings, with a particular emphasis on measuring outcomes in longitudinal epidemiologic studies and prevention or intervention trials. The battery has been normed and validated across the lifespan in subjects age 3-85 and its use ensures that assessment methods and results can be used for comparisons across existing and future studies. By providing a “common currency” for the study of neurological research, the NIH Toolbox enables economies of scale and enhances efficiency. The NIH Toolbox is capable of monitoring neurological and behavioral function over time, and measuring key constructs across developmental stages.

Scores from the NIH Toolbox Cognition Battery will produce a Cognitive Function Composite Score. Individual measure scores reflecting Executive Function, Attention, Episodic Memory, Language, Vocabulary, Processing Speed and Working Memory will also be obtained.

NIH Toolbox Cognition Battery (NIHTB-CB)

Vocabulary

NIH Toolbox Picture Vocabulary Test

Memory

NIH Toolbox Auditory Verbal Learning Test (Rey)

NIH Toolbox Picture Sequence Memory Test

Attention/Executive Functioning

NIH Toolbox Flanker Inhibitory Control and Attention

Test

NIH Toolbox Dimensional Change Card Sort Test

(DCCS)

Processing Speed

NIH Toolbox Pattern Comparison Processing Speed

Test

Working Memory

NIH Toolbox List Sorting Working Memory Test

5.4.2 Emotion

Subjects will complete four paper and pencil self-administered questionnaires to evaluate quality of life, fatigue, depression, and anxiety.

Short Form 36 Health Survey (SF-36)

36-item, patient-reported survey assessing overall health status and quality of life (Appendix 4).⁴³

Multidimensional Assessment of Fatigue (MAS)

16 item scale used to measure fatigue according to four dimensions: degree/severity, distress that it causes, timing of fatigue, and its impact on ADLs (Appendix 5).⁴⁴

Beck Depression Inventory-II (BDI-II)

21 item self-report multiple choice inventory used to assess for depression (Appendix 6).⁴⁵

Beck Anxiety Inventory (BAI)

21-question multiple-choice self-report inventory that is used for measuring how the subject has been feeling in the last week, focusing primarily on somatic symptoms (Appendix 7).⁴⁶

5.4.3 Hearing

Words-In-Noise (WIN) Test

Measures a person's ability to recognize single words amid varying levels of background noise, measuring difficulty a person might have hearing in a noisy environment. A recorded voice tells the participant to listen and repeat words.

Background noise gets louder, reducing the signal-to-noise ratio.

Hearing Handicap Inventory Screening

10 questions to assess hearing impairment.

5.4.4 Restless Leg Syndrome (RLS)

Restless Leg Syndrome Rating Scale

10 questions to assess restless leg symptoms.

6. Schedule of Measurements

6.1 Summary Timeline

The schedule of measurements is summarized in **Table 1**. Following successful screening and signed informed consent, subjects will donate a unit of autologous red blood cells (Donation1). This will be followed 40-42 days later by the baseline 51-Chromium post-transfusion recovery study. Following the 24-hour post-chromium infusion blood draw, the subjects will be randomized to iron infusion or placebo (Iron infusion1). Five months \pm 4 weeks later, subjects will donate the second unit of autologous blood (Donation2). The second 51-Chromium post-transfusion recovery study will be performed 40-42 days after this donation. Subjects will have to return 24-hours after chromium infusion to determine the 24-hour post-transfusion recovery. Surveys and neurocognitive assessments will be conducted prior to Donation1, PTR1, Donation2, and PTR2.

Because an active type and screen must be obtained before the blood bank issues the stored RBC unit and the radioactive 51-Cr-labeling can occur, we will provide subjects with the option of coming in up to 30 days prior to the scheduled PTR study to obtain a type and screen sample (1 tube of blood by standard venipuncture). This will provide for a shorter day for the PTR study because there will no longer be the need to wait for the type and screen testing and the study can begin once the subject arrives. If a subject chooses not to provide this optional blood draw, a blood sample will be taken when the IV lines are placed for the PTR study and the PTR study will proceed after the blood bank issues the blood and it is radiolabeled per hospital guidelines.

Table 1: Schedule of Measurements

Day of study	Urine pregnancy test	CBC with reticulocyte count	Iron parameters*	C-reactive protein	Type and Screen	51-Cr PTR**	Iron/Placebo infusion	Surveys/Neuro-cognitive	Metabolomics****
Screening		X	X	X	X				
Donation1	X	X	X	X				X	X
Blood draw (optional)***					X				
PTR1 (40-42 days after Donation1)	X	X	X	X	X	X		X	
Iron infusion1 (1 day after PTR1)	X						X		
Donation2 (5months ± 4 weeks after iron infusion1)	X	X	X	X				X	X
Blood Draw (optional)***					X				
PTR2 (40-42 days after Donation2)	X	X	X	X	X	X		X	
Final blood draw (1 day after PTR2)						X – collection of 24 hour (+/- 4hr) time point for final measurement			

*Iron parameters = Zinc Protoporphyrin (ZPP), iron, total iron binding capacity (TIBC), transferrin saturation, ferritin, soluble transferrin receptor, hepcidin.

**PTR = post-transfusion recovery study with associated blood draws for hemoglobin and Chromium-51 determination taken pre-infusion and 5, 7.5, 10, 12.5, 15, 30, 60 minutes and 24-hours post-infusion (+/- 4 hours).

***The option to come in up to 30 days prior to the PTR study will be provided to obtain a type and screen sample. This will provide an active type and screen specimen so that the PTR study can begin without delay. Alternatively, the type and screen blood sample will be drawn when the IV is paced for the PTR study and then the study will begin once the type and screen is tested and the blood is issued and labeled.

****Metabolomics will be performed by mass spectrometry on blood obtained from the unit at the time of radiolabeling by metabolomics facilities at BloodWorks NW and University of Colorado.

6.2 Assessment Procedures

6.2.1 Zinc Protoporphyrin, Serum Iron, Total Iron Binding Capacity, Transferrin Saturation, Ferritin, C-Reactive Protein, Soluble Transferrin Receptor

Samples for zinc protoporphyrin and soluble transferrin receptor will be sent to ARUP Laboratories for testing. The other parameters will be measured in the Columbia University Medical Center Automated Core Laboratory using clinically-validated instruments.

6.2.2 Hepcidin

This will be measured using an ELISA kit (Bachem) following the manufacturer's instructions.

6.2.3 Complete Blood Counts

Blood counts will be performed in the Columbia University Medical Center Automated Core Laboratory using clinically-validated instruments.

6.2.4 Urine Pregnancy Test

Point of care urine pregnancy testing will be performed using QuickVue One-Step hCG Urine tests (Quidel Corp) following the manufacturer's instructions.

6.2.5 Type and Screen Testing

All type and screen testing will be performed by licensed medical technologists in the Columbia University Medical Center – New York Presbyterian Hospital blood bank following standard procedures.

6.2.6 Metabolomics Testing

Comprehensive metabolomics testing will be performed for research use only at the metabolomics core facilities at the University of Denver and Bloodworks NW using coded specimens. CUIMC investigators will not share identifying information with the collaborating investigators.

7. Specimen Collection Procedures

All blood samples will be obtained by peripheral venipuncture or from an indwelling peripheral intravenous line following institutional protocols.

8. Compensation

Subjects will be provided monetary compensation in cash for participation per visit. \$20 will be provided for the screening. \$10 will be provided for re-screening for those who meet criteria to be invited to be screened again. \$80 will be provided for each donation and PTR study (\$320 total). \$80 will be provided for the iron/placebo infusion and for the final blood draw at the end of the study (\$160 total). Finally, \$40 will be provided for each of the optional blood draws. Thus, the maximum total compensation for subjects is \$590 and the minimum compensation is \$500 for completing the study. Subjects who dropout of the study prior to completion will keep any compensation received up to the dropout.

9. Adverse Event Criteria and Reporting

9.1 Definitions

Adverse Event (AE) – Any untoward or unfavorable medical occurrence in a human subject, including any abnormal sign (for example, abnormal physical exam or laboratory finding), symptom, or disease, temporally associated with the subject's participation in the research, whether or not considered related to the subject's participation in the research.

Grades were developed using the following guidelines:

Grade 1: Mild; asymptomatic or mild symptoms; clinical or diagnostic observations only; intervention not indicated.

Grade 2: Moderate; minimal, local or noninvasive intervention indicated; limiting age-appropriate instrumental ADL.

Grade 3: Severe or medically significant but not immediately life-threatening; hospitalization or prolongation of hospitalization indicated; disabling; limiting self care ADL.

Grade 4: Life-threatening consequences; urgent intervention indicated.

Grade 5: Death related to AE.

Serious Adverse Event (SAE) – Any adverse event temporally associated with the subject's participation in

research that meets any of the following criteria: results in death; is life-threatening (places the subject at immediate risk of death from the event as it occurs); requires inpatient hospitalization or prolongation of existing hospitalization; results in a persistent or significant disability/incapacity; results in a congenital anomaly/birth defect; or any other adverse event that, based upon appropriate medical judgment, may jeopardize the subject's health and may require medical or surgical intervention to prevent one of the other outcomes listed in this definition.

Note that seriousness and severity are separate concepts. The term "severe" refers to the intensity of a specific event; a severe event may be of minor medical significance (e.g., a severe leg cramp). The term "serious" is based on outcome or action criteria that are usually associated with events that pose a threat to the patient's life or functioning. An event that is mild in severity is serious if it leads to one of the outcomes defined above.

Grade 4 and 5 events will always be considered Serious Adverse Events. Many Grade 3 events and some Grade 1 and 2 events may meet the definition of a Serious Adverse Event.

Unexpected Adverse Event – Any adverse event occurring in one or more subjects in a research protocol, the nature, severity, or frequency of which is not consistent with either: the known or foreseeable risk of adverse events associated with the procedures involved in the research that are described in (a) the protocol-related documents, such as the IRB-approved research protocol or the current IRB-approved informed consent document, and (b) other relevant sources of information, such as product labeling and package inserts; or the expected natural progression of any underlying disease, disorder, or condition of the subject(s) experiencing the adverse event and the subject's predisposing risk factor profile for the adverse event.

Unanticipated problem involving risks to subjects or others (UP): Any incident, experience, or outcome that meets all of the following criteria: unexpected (in terms of nature,

severity, or frequency) given (a) the research procedures that are described in the protocol-related

Attribution – the determination of whether an adverse event is related to a medical treatment procedure.

Attribution categories:

1. Not Related - Event clearly related to other factors (e.g., clinical state, other therapies; concomitant drugs)
2. Possibly Related - Sequence of event is compatible with study drug, device, or procedure, but could have been produced by other factors
3. Probably Related - Sequence of event is compatible with study drug, device, or procedure and cannot be explained by other factors without much doubt
4. Definitely Related - Sequence of event is compatible with study drug, device, or procedure and beyond doubt cannot be explained by other factors

9.2 Types of Adverse Events Reported

Strict definitions and monitoring protocols of adverse effects (AEs) and serious AEs (SAEs) will be developed with the Data Safety Monitoring Board (DSMB). An SAE defined as being one or more of the following: (i) life threatening, (ii) results in hospitalization, or (iii) causes irreversible, persistent, or significant disability/incapacity; these will be reported to regulatory agencies within 7 days of their occurrence. Any AE or SAE temporally related with study procedures will be reported by the site investigators or coordinators. An alert will be sent to the DSMB, and the Institutional Review Board and Sponsor (NIH-NHLBI). Safety outcomes will be assessed at each study visit and with a follow-up phone call the day after each visit using a checklist of known adverse events and an open-ended question for volunteers to describe other adverse events. Participants will be encouraged to call the coordinator throughout the study if they experience 1) a new symptom, 2) change in severity of an existing symptom, 3) see a doctor/ER, 4) start a new medication. The most common serious acute adverse reaction of blood donation and insertions of intravenous lines is a vasovagal reaction, which may lead to loss of consciousness. Witnessed or un-witnessed vasovagal reactions will be considered as AEs, unless resulting in hospitalization (e.g., due to loss of consciousness causing

head trauma), in which case the event will be considered an SAE. Permanent or persistent peripheral arm nerve damage (in a phlebotomized arm) causing disability will be considered an SAE. Bruising and pain at the site of needle insertion that results in volunteer complaint at the follow-up phone call a day after phlebotomy will be considered an AE. Anaphylactoid reactions to iron infusions are usually evident within a few minutes, and close observation is necessary to ensure recognition. If at any time during the intravenous administration, any signs of a hypersensitivity reaction or intolerance are detected, administration will be stopped immediately. The reaction will be considered an SAE if it meets one of the criteria listed above. Furthermore, subjects will be called one day and one week after infusion to inquire about delayed side effects, such as myalgias, arthralgias, and gastrointestinal problems. Finally, iron deficiency is associated with fatigue, restless leg syndrome, decreased physical endurance and work capacity, and impaired concentration, attention, and other cognitive functions. Thus, subjects randomized to the placebo group may have AEs due to continued iron deficiency. These will be assessed using the validated Multidimensional Assessment of Fatigue, Beck Depression Inventory-II, Beck Anxiety Inventory, and the overall well-being SF-36 Health Survey incorporating both physical and mental summary measures. Each subject will take these short surveys as outlined in Table 1.

Medical follow-up of any Serious Adverse Event will be provided by the medical staff of Columbia University Medical Center in the New York Presbyterian Hospital or, if needed, in the out-patient clinic at appropriate intervals until resolution of the condition related to the Serious Adverse Event. An Adverse Event that does not meet the criteria of a Serious Adverse Event will be reported promptly to Drs. [name] and [name], appropriate management will be provided by the medical staff at Columbia University Medical Center, and the occurrence of any adverse events reviewed periodically by [name], [name], and their Co-Investigators. A Data Safety Monitoring Board will be established and will review all reported events at least annually and all serious adverse events within one month of occurrence. A report summarizing the Data Safety Monitoring Board meeting and

recommendations will be submitted to the Institutional Review Board.

9.3 Reporting timelines

Table 2 below details the SAE and UP safety reporting requirements and timelines. Reporting timelines for all non-serious AEs will follow the Data and Safety Monitoring Plan for the study.

Table 2: SAE and UP event reporting timelines

What Event is Reported	When is Event Reported	By Whom is Event Reported	To Whom is Event Reported
Fatal or life-threatening unexpected, suspected serious adverse reactions	Within 7 calendar days of initial receipt of information	Investigator	Local/internal IRBs and Data Safety Monitoring Board (DSMB)
		Sponsor	NHLBI
Non-fatal, non-life-threatening unexpected, suspected serious adverse reactions	Within 15 calendar days of initial receipt of information	Investigator	Local/internal IRBs and Data Safety Monitoring Board (DSMB)
		Sponsor	NHLBI
Unanticipated adverse effects	Within 10 working days of investigator first learning of effect	Investigator	Local/internal IRBs and Data Safety Monitoring Board (DSMB)
		Sponsor	Local/internal IRBs and Data Safety Monitoring Board (DSMB)
Unanticipated Problem that is not an SAE	Within 14 days of the investigator becoming aware of the problem	Investigator	Local/internal IRBs/Institutional Officials, NHLBI and/or DCC
All Unanticipated Problems ¹	Within 30 days of the IRB's receipt of the report of the UP from the investigator.	IRB	OHRP
		Investigator	External IRBs

¹ Per OHRP guidance: only when a particular AE or series of AEs is determined to meet the criteria for an UP should a report of the AE(s) be submitted to the IRB at each institution under the HHS regulations at 45 CFR part 46. Typically, such reports to the IRBs are submitted by investigators.

10. Interim Reporting

This section describes scheduled reports that will be sent to the DSMB. Reporting requirements for events that will be monitored continuously (i.e. all fatal events and all serious adverse events possibly, probably, or definitely related to red cell transfusion) are described above.

10.1 Semi-Annual DSMB Reports

The DSMB will meet twice a year, either in-person or via teleconference. Reports will include:

- Baseline characteristics overall and by group
- Primary study endpoint overall and by group, (p-values to compare to early stopping boundary will only be provided after 20, 40, and 60 volunteers have been completed)
- Number, type, and severity of serious adverse events, overall and by treatment arm, with p-value for comparison of number of serious adverse events per group. This p-value will be compared to the p-value boundary from an alpha-spending approach approximating O'Brien-Fleming boundaries. No formal stopping rule is set for this comparison.
- Number, type, and severity of adverse events attributed as possibly, probably, definitely related to donation, iron or red cell infusion, overall and by treatment arm, with p-value for comparison of number of such adverse events per group. This p-value will be compared to the p-value boundary from an alpha-spending approach approximating O'Brien-Fleming boundaries. No formal stopping rule is set for this comparison.
- Proportion of subjects in each treatment arm with at least one serious adverse event possibly, probably, or definitely related to a donation, red cell or iron infusion, with p-value. This p-value will be compared to the p-value boundary from an alpha-spending approach approximating O'Brien-Fleming boundaries. No formal stopping rule is set for this comparison.
- Unexpected adverse events, and unanticipated problems overall and by treatment arm
- Site status

- Accrual
- Site/study compliance issues
- Data entry completeness and data QA

11. Statistical Considerations

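### The DSMB's scheduled by-arm comparison of non-serious adverse events is limited to procedure-attributed events, so it can leave out the placebo-arm harm that section 9.2 foresees

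*Combined protocol and SAP*

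**What the plan says.** Protocol section 10.1 lists the contents of the semi-annual DSMB report. Four safety lines are split by arm:

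- "Number, type, and severity of serious adverse events, overall and by treatment arm", with a p-value and no attribution filter.
- "Number, type, and severity of adverse events attributed as possibly, probably, definitely related to donation, iron or red cell infusion", with a p-value comparing the number of such events per group.
- The proportion of subjects with at least one related serious event, with a p-value.
- "Unexpected adverse events, and unanticipated problems overall and by treatment arm", with no p-value mentioned.

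The three p-values are set against an alpha-spending boundary, and section 10.1 says that none carries a formal stopping rule.

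Section 9.2 describes possible harms in each arm. For iron these are hypersensitivity reactions and delayed myalgias, arthralgias and gastrointestinal problems, asked about by telephone one day and one week after infusion. For placebo it says that "subjects randomized to the placebo group may have AEs due to continued iron deficiency", having just listed fatigue, restless legs, reduced endurance and work capacity, and impaired cognition. On measurement it says: "These will be assessed using the validated Multidimensional Assessment of Fatigue, Beck Depression Inventory-II, Beck Anxiety Inventory", together with the SF-36. The same section says that the DSMB "will review all reported events at least annually".

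Section 5.4.4 adds a restless-legs scale, "10 questions to assess restless leg symptoms", which is not among the four surveys in section 9.2.

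**The concern.** The trial selects donors with ferritin below 15 ng/mL and excludes anyone unwilling to stop iron supplements. Placebo subjects then wait five months, give or take four weeks, donate another unit, and have the second recovery study 40 to 42 days after that. For them the foreseeable harm comes from going without iron, not from a procedure.

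The scheduled comparison of non-serious events admits an event only if it is attributed to donation, iron or red cell infusion. Iron reactions fit that filter easily. Events from continued deficiency fit it only if an assessor links them to a procedure. The DSMB's early-stopping criteria in section 11.3 include futility judged in the context of adverse events, so the balance of events between arms is something it will weigh. A table that takes in one arm's harm more readily than the other's is a weak basis for that judgement.

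**Working it through.** The plan states no figure on this point, so the main check sets the sections side by side.

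**Routes by which a non-serious event from continued iron deficiency could reach a by-arm line in section 10.1**

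1. *All serious events.* Open only if the event is serious.
2. *Related events.* Section 9.1 defines Not Related as clearly due to other factors and gives clinical state as an example. An event correctly judged to come from underlying iron deficiency can be coded there and is then not counted. Possibly Related requires only a sequence compatible with a study drug, device or procedure and allows other causes, so the same event could also be counted. The protocol does not say which coding applies to this harm.
3. *Related serious events.* Needs both seriousness and attribution.
4. *Unexpected events.* Section 9.1 defines these as inconsistent, in nature, severity or frequency, with known or foreseeable risk or with the expected course of an underlying condition. Section 9.2 foresees this harm, so it would normally enter only if worse or more frequent than foreseen.
5. *Surveys.* Section 9.2 uses them to assess this harm. No survey score is on the section 10.1 list.

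Only route 2 is regularly open to a non-serious event of foreseen severity, and it depends on attribution.

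**Time on placebo.** Taking a month as 30.4 days, the shortest span from infusion to the second recovery study is 5 × 30.4 − 28 + 40 = 164 days (5.4 months). The longest is 5 × 30.4 + 28 + 42 = 222 days (7.3 months).

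**Size, on assumed rates only.** Take n = 30 per arm (section 11.2) and two-sided alpha 0.05. Let p1 and p2 be the proportions of placebo and iron subjects with a fatigue-type event, and q the share attributed to a procedure, the same in both arms. The table then shows q·p1 against q·p2. With d the visible difference and p̄ the mean of the two visible proportions,

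power = Φ[(d − 1.96·SE0) / SE1], where SE0 = √(p̄(1 − p̄)·2/30) and SE1 = √([a(1 − a) + b(1 − b)]/30), with a = q·p1 and b = q·p2.

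For 40% v 10%:
- q = 1: SE0 = √(0.25 × 0.75 × 2/30) = 0.1118; SE1 = √((0.24 + 0.09)/30) = 0.1049; power = Φ[(0.30 − 0.2191)/0.1049] = Φ(0.77) = 0.78.
- q = 0.5: SE0 = √(0.125 × 0.875 × 2/30) = 0.0854; SE1 = √((0.16 + 0.0475)/30) = 0.0832; power = Φ[(0.15 − 0.1674)/0.0832] = Φ(−0.21) = 0.42.

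| Assumed rates, placebo v iron | Share attributed | Expected subjects shown | Approximate power |
|---|---|---|---|
| 40% v 10% | all | 12 v 3 | 78% |
| 40% v 10% | half | 6 v 1.5 | 42% |
| 40% v 10% | quarter | 3 v 0.75 | 22% |
| 30% v 10% | all | 9 v 3 | 49% |
| 30% v 10% | half | 4.5 v 1.5 | 25% |
| 30% v 10% | quarter | 2.25 v 0.75 | 14% |

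If none is attributed, nothing shows. The normal approximation is rough at such counts, and the table counts subjects whereas section 10.1 compares numbers of events.

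A second, purely assumed example concerns direction. Suppose 5 of 30 iron subjects have infusion-related events and 8 of 30 placebo subjects have deficiency-related events. The table reads 5 v 0 if none of the 8 is attributed to a procedure and 5 v 8 if all are counted. Fisher's exact two-sided p is 0.052 and 0.53 respectively. Neither is significant at 0.05, but the direction of the difference reverses.

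**The case against.** A reader might infer that the placebo-arm harm is removed by construction and that the DSMB would never see it. The documents do not support either statement.

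- Attribution is blinded (section 4.3), every subject gives study donations and receives an infusion, and Possibly Related is a broad category. Fatigue after a donation or infusion may well be counted. Loss is possible, not built in.
- Section 9.2 has the DSMB reviewing all reported events at least annually, with no attribution filter. The randomization scheme goes to the DSMB (section 4.2) and its statistician is unblinded (section 4.3), so it could split events by arm if it chose.
- The unexpected-event line is also shown by arm and could take in a foreseen harm of unforeseen severity or frequency.
- Fatigue and wellbeing are compared between arms in section 11.1, and depression, anxiety and cognition are secondary hypotheses in section 2.2.
- Section 9.3 refers to a separate Data and Safety Monitoring Plan, which is not in the documents and might add tables.
- No formal stopping rule attaches to this comparison, so a wrong stopping decision is conjecture.

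All of this stands and limits the point. It does not close the gap. The annual review has no stated by-arm format, and a harm expected mainly in one arm needs an arm comparison. The section 11.1 comparisons are not on the DSMB's report list. The separate plan is cited only for reporting timelines. The restless-legs scale appears in neither section 2.2 nor section 11.1.

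**Conclusion.** The point holds in a limited form. The scheduled by-arm report has no line for all non-serious adverse events regardless of attribution, and it lists none of the surveys that section 9.2 assigns to the placebo-arm harm. Whether events from continued iron deficiency enter the arm comparison therefore rests on blinded attribution, which the protocol does not settle for this harm. The gap lies in the scheduled comparison, not in everything the DSMB can see.

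Its size cannot be derived from the documents. On the assumed rates, counting half of the events instead of all roughly halves the power, from 78% to 42% or from 49% to 25%. The 5 v 0 against 5 v 8 example shows only that direction can depend on the filter; it is not a forecast. The conclusion assumes that the section 10.1 list is the report the DSMB will receive and that no unseen plan adds an all-cause table. It is a worthwhile low-cost improvement and does not affect the validity of the primary analysis.

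**What to change.** 1. In section 10.1, tabulate all non-serious adverse events by arm regardless of attribution and put the p-value on that table. Keep the related events as a subset table.
2. Add to the closed DSMB report descriptive by-arm summaries, without p-values, of the four surveys named in section 9.2 and of the restless-legs scale in section 5.4.4. Routine by-arm cognitive test summaries are optional and are not needed to close the gap.
3. Reconcile section 10.1 with the statement in section 9.2 that the DSMB reviews all reported events, saying whether that review is by arm.

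The cost is revised wording in two sections and a few more tables from data already collected, with no new visits or tests. There are two drawbacks. Unrelated background events enter the main table, adding noise that randomization balances on average. The DSMB also sees survey outcomes at interim, which is why those summaries should be descriptive only.
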